17.5 Reporting of Adverse Events and New Information

Describe how adverse events and other information will be reported from the clinical sites to the overall study director. Provide the timeframe for this reporting.

[name] will report AEs, SAEs, UPS and protocol deviations to IRB and [name] as soon as feasible. Reports to the SO and the NIAMS will be performed as outlined in section 18.

17.6 Audit and Monitoring Plans

Describe the process to ensure all local site investigators conduct the study appropriately. Describe any on-site auditing and monitoring plans for the study.

[name], Data Management Specialist, Department of Public Health Sciences, will perform audits to ensure data collection instruments and procedures are performed according to the good clinical practice guidelines.

18.0 Adverse Event Reporting

18.1 Adverse Event Definitions

For device studies, incorporate the following definitions into the below responses, as written:	
Unanticipated adverse device effect	Any serious adverse effect on health or safety or any life-threatening problem or death caused by, or associated with, a device, if that effect, problem, or death was not previously identified in nature, severity, or degree of incidence in the investigational plan or IDE application (including a supplementary plan or application), or any other unanticipated serious problem associated with a device that relates to the rights, safety, or welfare of subjects.

18.2 Recording of Adverse Events

Address the frequency and process for eliciting adverse event information from research subject, e.g., "Research subjects will be routinely questioned about adverse events at study visits."

In the response, incorporate the following as written:

All adverse events (serious or non-serious) and abnormal test findings observed or reported to study team believed to be associated with the study drug(s) or device(s) will be followed until the event (or its sequelae) or the abnormal test finding resolves or stabilizes at a level acceptable to the investigator.

An abnormal test finding will be classified as an adverse event if one or more of the following criteria are met:

- The test finding is accompanied by clinical symptoms
- The test finding necessitates additional diagnostic evaluation(s) or medical/surgical intervention; including significant additional concomitant drug treatment or other therapy

NOTE: Simply repeating a test finding, in the absence of any of the other listed criteria, does not constitute an adverse event.

- The test finding leads to a change in study drug dosing or discontinuation of subject participation in the clinical research study
- The test finding is considered an adverse event by the investigator.

Research subjects will be routinely evaluated by research team (part of the study team) during visits of the standard rehabilitation protocol.

All adverse events (serious or non-serious) and abnormal test findings observed or reported to study team believed to be associated with the study device(s) will be followed until the event (or its sequelae) or the abnormal test finding resolves or stabilizes at a level acceptable to the investigator.

An abnormal test finding will be classified as an adverse event if one or more of the following criteria are met:

- The test finding is accompanied by clinical symptoms
- The test finding necessitates additional diagnostic evaluation(s) or medical/surgical intervention
- The test finding is considered an adverse event by the investigator.

18.3 Causality and Severity Assessments

By submitting this study for review, you agree to the following statement – DO NOT ALTER OR DELETE:

The investigator will promptly review documented adverse events and abnormal test findings to determine 1) if the abnormal test finding should be classified as an adverse event; 2) if there is a reasonable possibility that the adverse event was caused by the study device(s); and 3) if the adverse event meets the criteria for a serious adverse event.

If the investigator's final determination of causality is "unknown and of questionable relationship to the study device(s)", the adverse event will be classified as associated with the use of the study device(s) for reporting purposes. If the investigator's final determination of causality is "unknown but not related to the study device(s)", this determination and the rationale for the determination will be documented in the respective subject's case history.

18.4 Reporting of Adverse Reactions and Unanticipated Problems to the FDA

18.4.1 Written IND/IDE Safety Reports

For a drug study under an IND, incorporate the following from 21 CFR 312.32 as written – DO NOT ALTER OR DELETE:

The Sponsor-Investigator will submit a written IND Safety Report (i.e., completed FDA Form 3500A) to the responsible new drug review division of the FDA for any observed or volunteered adverse event that is determined to be a serious and unexpected, suspected adverse reaction. Each IND Safety Report will be prominently labeled, "IND Safety Report", and a copy will be provided to all participating investigators (if applicable) and sub-investigators.

Written IND Safety Reports will be submitted to the FDA as soon as possible and, in no event, later than 15 calendar days following the Sponsor-Investigator's receipt of the respective adverse event information and determination that it meets the respective criteria for reporting.

For each written IND Safety Report, the Sponsor-Investigator will identify all previously submitted IND Safety Reports that addressed a similar suspected adverse reaction experience and will provide an analysis of the significance of newly reported, suspected adverse reaction in light of the previous, similar report(s) or any other relevant information.

Relevant follow-up information to an IND Safety Report will be submitted to the applicable review division of the FDA as soon as the information is available and will be identified as such (i.e., "Follow-up IND Safety Report").

If the results of the Sponsor-Investigator's follow-up investigation show that an adverse event that was initially determined to not require a written IND Safety Report does, in fact, meet the requirements for reporting; the Sponsor-Investigator will submit a written IND Safety Report as soon as possible, but in no event later than 15 calendar days, after the determination was made.

For a device study under an IDE, incorporate the following from 21 CFR 812.150 as written – DO NOT ALTER OR DELETE:

The Sponsor-Investigator will submit a completed FDA Form 3500A to the FDA's Center for Devices and Radiological Health for any observed or volunteered adverse effect that is determined to be an unanticipated adverse device effect. A copy of this completed form will be provided to all participating sub-investigators.

The completed FDA Form 3500A will be submitted to the FDA as soon as possible and, in no event, later than 10 working days after the Sponsor-Investigator first receives notice of the adverse effect.

If the results of the Sponsor-Investigator's follow-up evaluation show that an adverse effect that was initially determined to not constitute an unanticipated adverse device effect does, in fact, meet the requirements for reporting; the Sponsor-Investigator will submit a completed FDA Form 3500A as soon as possible, but in no event later than 10 working days, after the determination was made.

For each submitted FDA Form 3500A, the Sponsor-Investigator will identify all previously submitted reports that addressed a similar adverse effect experience and will provide an analysis of the significance of newly reported adverse effect in light of the previous, similar report(s).

Subsequent to the initial submission of a completed FDA Form 3500A, the Sponsor-Investigator will submit additional information concerning the reported adverse effect as requested by the FDA.

Not applicable

18.4.2 Telephoned IND Safety Reports – Fatal or Life-threatening Suspected Adverse Reactions

For a drug study under an IND, incorporate the following from 21 CFR 312.32 into the response, as written:

In addition to the subsequent submission of a written IND Safety Report (i.e., completed FDA Form 3500A), the Sponsor-Investigator will notify the responsible review division of the FDA by telephone or facsimile transmission of any unexpected, fatal or life-threatening suspected adverse reaction.

The telephone or facsimile transmission of applicable IND Safety Reports will be made as soon as possible but in no event later than 7 calendar days after the Sponsor-Investigator's receipt of the respective adverse event information and determination that it meets the respective criteria for reporting.

Not applicable

18.5 Reporting Adverse Reactions and Unanticipated Problems to the Responsible IRB

By submitting this study for review, you agree to the following statement – DO NOT ALTER OR DELETE:

In accordance with applicable policies of The Pennsylvania State University Institutional Review Board (IRB), the investigator will report, to the IRB, any observed or reported harm (adverse event) experienced by a subject or other individual, which in the opinion of the investigator is determined to be (1) unexpected; and (2) probably related to the research procedures. Harms (adverse events) will be submitted to the IRB in accordance with the IRB policies and procedures.

18.6 Reporting AEs, SAEs and UPs to the NIAMS and the SO

- AEs will be reported in aggregate in the biannual report to the safety officer.
- The PIs will report SAEs to IRB, the Safety Officer and the NIAMS, through the NIAMS Executive Secretary, within 48 hours of becoming known by the PI.
- The PI will notify all Ups to the PSU IRB, the SO, and the NIAMS within 48 hours of the initial notification.

- Protocol deviations impacting participant safety should be reported to the NIAMS and the SO (through the NIAMS Executive Secretary) within 48 hours of the investigator becoming aware of the event; all other deviations that do not impact participant safety should be reported as part of the routine DSM report

18.7 Unblinding Procedures

Describe the procedures for unblinding study therapy on a subject, including documentation of this in the subject's source document. Include example(s) here why someone might unblind a study. In most cases, the unblinding will be part of managing a serious adverse reaction and will be reported with the serious adverse event. However, in cases where unblinding was not associated with a serious adverse event, such actions should be reported in a timely manner.

Not applicable

18.8 Stopping Rules

In studies with a primary safety endpoint or studies with high risk to study subjects, provide the rules that define the circumstances and procedures for interrupting or stopping the study. If an independent Data and Safety Monitoring (DSMB) or Committee (DSMC) is set up for the study, the same stopping rules should be incorporated into the safety analysis plan as well.

The study will be interrupted if AEs (re-rupture, deep venous thrombosis, infections, and skin irritation) occur at a rate higher than that reported for standard of care.

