8.3 Statistical methods

Describe the statistical methods (or non-statistical methods of analysis) that will be employed.

We will recruit 25 participants to participate in the NMES intervention and 25 for standard rehabilitation (control). Summary statistics for variables of interest including recruitment, retention, adherence, and reported pain will be calculated. To test the difference between groups (NMES and control), we will quantify the odds ratio and the 95% confidence interval of performing a single heel-rise test. If the bottom end of the confidence interval is higher than 1.0, the improvement will be significant. Chi-square goodness of fit will be used to study the associations between groups and covariates such as gender, activity, and age. Cochran-Mantel-Haenszel test will be used to evaluate the consistency of such associations.

Protocol deviations, such as missing visits, or lost to follow up (within the 10% already considered in the power analysis) will have a negligible effect on the statistical analysis since the proposed analysis can have unbalanced groups. The planned interim safety analyses will quantify the odds ratio between adverse events in the intervention group and standard of care. If the bottom end of the confidence interval is higher than 1.0, the incidence of AEs in the intervention group will be significant higher than that of standard care.

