9.1 Periodic evaluation of data

Describe the plan to periodically evaluate the data collected regarding both harms and benefits to determine whether subjects remain safe.

The research team will monitor the recovery of the participant during standard-of-care visits and determine the occurrence of possible adverse related to Achilles tendon healing (re-rupture, deep vein thrombosis, deep and superficial infection) or the use of NMES (skin irritation and excessive pain).

Research team will capture and report all AEs at every visit. These AEs will be evaluated by a physician study team member ([name]) for their relatedness and severity. If the team member physician ([name]) prescribes a modification in the rehabilitation protocol or additional interventions (surgery), the patient will be removed from the study. Cumulative data will be evaluated every 2 months to determine if incidence of adverse events is higher than the normal (standard of care). The normal (standard of care) incidence of re-ruptures is 5% [4], [25], deep vein thrombosis is 48% [61], infection 2.8% [62], skin irritation 33% [63].

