9.7 Statistical tests

Describe the statistical tests for analyzing the safety data to determine whether harms are occurring.

For testing the difference groups and standard treatment, we will quantify the odds ratio and the 95% confidence of AEs or SAEs. If the bottom end of the confidence interval is higher than 1.0, the improvement will be significant.

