9.8 Suspension of research

Describe any conditions that trigger an immediate suspension of research.

If the odds ratio of AEs related to the intervention and/or SAEs of the intervention reaches statistical significant levels compared to standard treatment, the study will be suspended immediately.

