10.0 Risks

List the reasonably foreseeable risks, discomforts, hazards, or inconveniences to the subjects related to the subjects' participation in the research. Include as may be useful for the IRB's consideration, a description of the probability, magnitude, duration and reversibility of the risks. Consider all types of risk including physical, psychological, social, legal, and economic risks. Note: Loss of confidentiality is a potential risk when conducting human subject research.

- If applicable, indicate which procedures may have risks to the subjects that are currently unforeseeable.
- If applicable, indicate which procedures may have risks to an embryo or fetus should the subject be or become pregnant.
- If applicable, describe risks to others who are not subjects.

Risk of Randomization: You will be assigned to a treatment program by chance. The treatment you receive may prove to be less effective or to have more side effects than the other research treatment(s) or other available treatments.

Heel-rise test: The heel-rise testing may cause local tendon pain. The subjects will be informed that if they have a pain level above a 5/10 they should inform the evaluator, stop the test, and avoid strong physical activity for 1 or 2 days.

NMES usage: The device used for this test is FDA approved. There is a minimal risk of infection. Discomfort during and muscle soreness after usage lasting a few days after the test may be experienced. Skin irritation caused by the adhesive pads may also occur. Excessive pain might occur during stimulation, even at the recommended settings. Subjects will be instructed to gradually increase the stimulation intensity up to the recommended level by PT. Subjects will be instructed to contact the research team if the excessive pain occurs at or below the recommended intensity.

Tendon healing: Re-injury of the tendon is also a potential risk. The rate of tendon re-rupture in standard therapy is estimated between 2% and 5% [64]. Gapping or non-healing of the tendon have also been observed in regular therapy. These adverse events may be observed in the participants participating in the study. Statistical analysis will be performed to determine if the risk of these adverse events is higher in the intervention group compared to standard therapy.

Additional Risks

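### Section 18.8 interrupts the study whenever a raw adverse-event rate exceeds the published one, with no allowance for chance, no denominator and no link to the odds-ratio rule in 9.7 and 9.8

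*Combined protocol and SAP*

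**What the plan says.** Section 18.8 (Stopping Rules) is mandatory in tone: "The study will be interrupted if AEs (re-rupture, deep venous thrombosis, infections, and skin irritation) occur at a rate higher than that reported" for standard care. It gives no denominator, minimum count, margin or confidence level. It does not say whether the four events are judged separately or together, what an interruption pauses, or who lifts it.

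The published rates are in 9.1: "incidence of re-ruptures is 5% [4], [25], deep vein thrombosis is 48% [61], infection 2.8% [62], skin irritation 33% [63"]. The same section sets the schedule: "Cumulative data will be evaluated every 2 months to determine if incidence of adverse events is higher than the normal (standard of care"). No test is named there either.

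A second rule appears elsewhere. Section 9.7 calls for an odds ratio with a 95% interval, and 9.8 acts on it: "If the odds ratio of AEs related to the intervention and/or SAEs of the intervention reaches statistical significant levels compared to standard treatment", the study is suspended at once. Section 8.3 describes the same interval for the interim safety analyses and reads a lower limit above 1.0 as showing that "the incidence of AEs in the intervention group will be significant higher than that of standard care". Section 10.0 adds: "Statistical analysis will be performed to determine if the risk of these adverse events is higher in the intervention group compared to standard therapy". None of these sections refers to 18.8, and 18.8 refers to none of them.

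**The concern.** When the true rate equals a fixed benchmark, the observed rate exceeds it a large part of the time by chance alone. With four events, each able to trigger, and repeated reviews, such a rule would fire in most trials of a harmless treatment and could not separate harm from chance. The team would have to halt a 50-person trial without cause or set aside a rule it had committed to.

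The two rules also use different comparators, published rates in 18.8 and the concurrent control arm in 9.8. They can therefore give opposite answers on the same data, and the plan does not say how they relate.

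**Working it through.** **Inputs.** Benchmarks from 9.1: re-rupture 5%, DVT 48%, infection 2.8%, skin irritation 33%. Arm size 25 from 8.3 (8.2: 22 / 0.9 = 24.4, rounded up to 25). The plan states no error rate for 18.8, so there is no figure of its own to reproduce.

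**1. Each event alone, one look, NMES arm.** The trigger is the smallest count r with r/25 above the benchmark p, that is r = floor(25p) + 1. The false-trigger probability is P(X ≥ r) for X ~ Binomial(25, p).

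| Event | 25p | r | P(X ≥ r) |
|---|---|---|---|
| Re-rupture | 1.25 | 2 | 0.358 |
| DVT | 12.0 | 13 | 0.420 |
| Infection | 0.70 | 1 | 0.508 |
| Skin irritation | 8.25 | 9 | 0.448 |

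**2. Any of the four, events independent.** 1 − (0.642 × 0.580 × 0.492 × 0.552) = 0.899. With 22 participants it is 0.898.

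**3. Sensitivity of the per-event reading.**
- DVT never triggers: 1 − (0.642 × 0.492 × 0.552) = 0.826.
- DVT never triggers and true re-rupture is 2% (judged against 5%): P(X ≥ 2) = 0.089, so 1 − (0.911 × 0.492 × 0.552) = 0.753.
- All true rates half the benchmarks: 0.398.
- Events positively correlated within participants: 0.78 to 0.89. Under any dependence the figure is at least 0.508, the infection component alone.
- All 50 as denominator, irritation in the NMES arm only: 0.82. If DVT also never triggers, 0.68; with true re-rupture also 2%, 0.46.

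**4. Pooled reading, one look.**
- Total events: 25 × (0.05 + 0.48 + 0.028 + 0.33) = 22.2, so the trigger is 23 and the probability 0.463.
- Participants with any event: benchmark 1 − (0.95 × 0.52 × 0.972 × 0.67) = 0.678; 25 × 0.678 = 16.96, so the trigger is 17 and the probability 0.587.
- Same triggers with observed DVT at an assumed 10%: 0.002 for total events and 0.015 for participants with any event.

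**5. Odds-ratio reading.** 25 against 25, both arms at benchmark, any of four, one look: 2.9% with Fisher's test, and 4.1% or 4.7% with a Wald interval, depending on how 0.5 is added for zero cells.

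**6. The two rules on the same data.** One NMES infection gives 1/25 = 4%, above 2.8%, so 18.8 fires. Against 0/25 in control, Fisher p = 1.0, so 9.8 does not. With no control infections, five NMES infections give p = 0.0502, so six are needed. The rules differ by one event against six.

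**7. Repeated looks (simulation, benchmark rates).** The protocol's looks are two-monthly. Looks by participant count are assumed here because accrual timing is not given. The per-event reading gives 96% with looks at 13 and 25, and 99% with looks after every 5. Over five looks the pooled readings give 75% to 78% (DVT at 48%) and the odds-ratio test 9%.

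**8. A rule that allows for chance.** Requiring a one-sided 95% exact lower limit above the benchmark at n = 25 means at least 4 re-ruptures, 17 DVTs, 3 infections or 13 skin irritations. The one-look false-interruption probability is then 13%. At 97.5% the counts are 5, 18, 4 and 14, and the probability is 4%.

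**The case against.** The strongest reply is that a coherent two-layer scheme can be read into the plan. Section 18.8 says interrupted and 9.8 says suspended, which suits a sensitive pause followed by a formal test. Sections 8.3, 9.7 and 10.0 all point to the odds ratio as the way to decide that harm is higher. The 18.8 template prompt is aimed at trials with a primary safety endpoint or high risk. This trial has no primary safety endpoint and uses a 510(k) device within its indications. A low trigger also errs toward caution, and the choice of threshold is partly preference.

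Much of that stands. Caution is legitimate, and the confidence level is for the safety officer and study physician to choose. But no text sets out the two layers or says what a pause entails. The reference in 18.8 to reported rates points to published figures, not to concurrent controls. However optional the section was, once written it binds.

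A second reply concerns DVT, and it also stands. The 48% benchmark dominates any pooled rate. No DVT screening is described, and section 2.3 expects NMES to lower DVT. A reader might infer that the rule misfires about half the time or more on every reading. The documents do not support that: the pooled figures fall to about 0.2% to 1.5% if observed DVT is 10%, and the odds-ratio reading gives 3% to 5%. The per-event result does not depend on DVT in this way.

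**Conclusion.** The rule is wrong as written and should be fixed. On its most direct reading (each event, NMES arm, published rate) it fires without added harm about 90% of the time at one look. Plausible changes in the inputs bring this to 83%, 75% or 40%. These figures assume 25 participants with complete follow-up, independent events and true rates at the stated values. The true DVT rate under NMES is not known.

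The high figure belongs to that reading alone. How far 18.8 misfires depends on a link between the rules that the plan leaves unstated, which is itself part of the defect.

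Two further inferences would go too far. Nothing here shows bias in the heel-rise analysis. Nor does the text say that an interruption ends the trial. Individual removal criteria (3.3.1), physician review of adverse events (9.1) and the safety officer (9.5) remain in place whatever 18.8 does.

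**What to change.** - State that 18.8 is a pause for safety officer review and 9.8 is suspension. Say what the pause covers and who lifts it.
- Define the 18.8 trigger per event on the NMES arm as explicit counts at each planned review, with an allowance for chance. The counts in working step 8 are an example. The safety officer and study physician should choose the level.
- Report false-interruption and detection probabilities over the planned two-monthly reviews.

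Minor tidying in the same edit: settle one re-rupture benchmark (section 10.0 has "The rate of tendon re-rupture in standard therapy is estimated between 2% and 5"%, which includes the 5% in 9.1). Describe the 33% irritation figure as an electrical-stimulation rate, since its reference is titled as a page on TENS complications. In 9.7, where a harmful result is described as "If the bottom end of the confidence interval is higher than 1.0, the improvement will be significant", use the 8.3 wording instead.

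The cost is protocol wording and a short simulation. The real price is sensitivity. Over five assumed looks, moving from the current per-event rule to the 95% or 97.5% limit changes:

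| Quantity | Current | 95% | 97.5% |
|---|---|---|---|
| False interruption, any of four | 99% | 27% | 12% |
| Detection, true re-rupture 20% | 99% | 80% | 69% |
| Detection, true re-rupture 10% | 85% | 30% | 20% |
| Detection, true infection 10% | 93% | 50% | 36% |

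Detection rows count the trigger for that event only. The loss for moderate harm is large. It is partly covered by 48-hour reporting of SAEs and unanticipated problems (18.6), physician review and the individual removal criteria. A more sensitive limit is defensible if its false-interruption probability is stated.
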